NBL	Nutritional Biomarker Laboratory
Non_CTIMP	Non-Clinical Trial of an Investigational Medicinal Product
PI	Principal Investigator
PID	Participant Identifiable Data
PPI	Participant and Public Involvement
REC	Research Ethics Committee
SAE	Serious Adverse Event
sFTP	Secure File Transfer Protocol
SOP	Standard Operating Procedure
SRD	Secure Research Domain
T2D	Type 2 diabetes
WLP	Weight loss programme

STUDY SUMMARY

Study Title	Supporting Weight Management (SWiM): Evaluating the effectiveness,		
	equity, and cost-effectiveness of using acceptance-based guided self-help		
	to improve long-term outcomes of weight management interventions		
Short title	SWiM 2.0		
Study Design	A randomised, single-blinded, parallel-group trial with 1:1 randomisation.		
Study Participants	The study will recruit 1,840 UK adults with overweight or obesity who have recently completed a behavioural weight management programme.		
	Participants will be recruited from five different UK-commissioned weight loss programmes (WLPs):		
	Tier 2 weight management programme		
	2. Tier 3 weight management programme		
	3. NHS Diabetes Prevention Programme		
	4. NHS Digital Weight Management Programme		
	5. NHS Diabetes Remission Programme		
	Eligibility Criteria Inclusion Criteria:		
	Age ≥18 years		
	 Capable of providing informed consent 		
	Good understanding of English		
	Willing to be randomised		
	Willing to complete study measurements		
	Able to access the web-based platform from home		
	Exclusion criteria		
	Current use of insulin		
	Previous or planned bariatric surgery		
	Current or planned pregnancy		
	Current diagnosis of an eating disorder		
	Participants will be recruited in collaboration with WLP providers, with targeted efforts to ensure diversity in recruitment. Oversampling will be used to ensure adequate representation of underserved groups, including men, people from minority ethnic backgrounds, and those from lower socioeconomic backgrounds.		

Research	Primary Research Question:
Question/Aim(s)	Does the SWiM intervention improve long-term weight maintenance, physical health, and mental well-being compared to standard care in adults who have recently completed a weight loss programme?
	Secondary Research Questions:
	 What is the impact of SWiM on long-term weight outcomes, glycaemic control, and psychological well-being, including depression, anxiety, emotional eating, and quality of life? Does the effectiveness of SWiM differ by initial weight loss programme?
	 What are the barriers and facilitators to engagement with SWiM, and how do they vary across demographic and socioeconomic groups? What is the cost-effectiveness of SWiM compared to standard care in maintaining weight loss and preventing type 2 diabetes and other obesity-related complications?
	 How can SWiM be adapted for people using GLP1-RA pharmacotherapy or bariatric surgery to support long-term weight maintenance?
Summary of study procedures	This is a randomised, single-blinded, parallel-group trial with 1:1 allocation to the SWiM intervention or standard care.
	 Recruitment: Participants who have completed a behavioural weight management programme within six months will be identified and enrolled. Randomisation: Stratified by weight loss programme and weight
	 loss medication use. Intervention: The SWiM group will access a web-based self-help programme with behavioural exercises and telephone coaching. A paper workbook will also be available.
	 Control: Standard care with no additional structured support. Assessments: Conducted remotely at baseline, 6, 12, and 24 months, measuring weight, glycaemic control, mental health, eating behaviours, and quality of life.
	 Process evaluation and economic analysis: A mixed-methods evaluation, including participant interviews, to assess engagement, feasibility, and cost-effectiveness. Follow-up: Two years to assess long-term weight maintenance, with
	Tollow-up. Two years to assess long-term weight maintenance, with

[figure not shown]
potential health record linkage for future outcomes.

STUDY FLOW CHART

1. BACKGROUND

Obesity and type 2 diabetes (T2D) represent significant public health challenges, with substantial impacts on physical and mental health, economic systems, and society. While behavioural weight loss interventions have been shown to produce clinically meaningful and cost-effective reductions in weight, sustaining these benefits remains a critical issue. Weight regain is common and undermines long-term health improvements, highlighting the need for interventions that support weight loss maintenance. 5,6

Weight loss maintenance programmes based on self-regulation can achieve modest improvements in long-term weight outcomes. However, to date, no UK-based trials have demonstrated effectiveness or cost-effectiveness of a weight loss maintenance programme. Hour systematic review and network meta-analysis found that incorporating strategies from Acceptance and Commitment Therapy (ACT) could have greater effects than standard behaviour change strategies. ACT¹³ is a psychological therapy approach that teaches people skills and strategies that directly address some of the core psychological challenges of maintaining weight loss, including acceptance and tolerance of aversive internal experiences (e.g., food cravings, physical discomfort, negative emotions), self-compassion to prevent discouragement following minor lapses, and reductions in negative mood and emotional eating. However, ACT-based interventions are typically used in-person and delivered by Clinical Psychologists, limiting their scalability and affordability in the UK NHS. Some randomised trials of digital ACT-based interventions for lifestyle modification have demonstrated acceptability and feasibility, with positive effects on eating behaviours and psychological flexibility, but their effects on weight and physical activity remain unclear. Activity remain unclear.

Using a rigorous theory-, evidence-, and person-based approach, ¹⁹⁻²¹ we developed an ACT-based guided self-help programme that addresses the specific challenges of weight loss maintenance. The Supporting Weight Management (SWiM) programme is delivered using an online web platform and telephone support from a trained non-specialist coach ^{22,23}. In our randomised controlled feasibility trial, ²⁴ we found that SWiM was feasible and engaging, and we observed promising effects on weight and psychosocial outcomes. However, a definitive randomised controlled trial is needed to evaluate the effect of SWiM on weight, physical health, and mental well-being following a range of behavioural programmes commissioned in the UK and to identify potential differential effectiveness by weight loss programme (WLP) and demographic groups. Detailed process evaluation is also needed to understand the mechanisms of action and contextual factors influencing the programme's impact. These insights will be critical for refining SWiM and developing guidance for its potential national implementation within NHS weight management services.

2. AIMS AND OBJECTIVES

2.1 Aim

To evaluate the effectiveness, equity, and cost-effectiveness of the SWiM programme relative to standard care in people who have recently completed a behavioural weight loss programme.

2.2 Objectives

Clinical Effectiveness

Primary Objective:

To evaluate the effect of SWiM versus standard care on weight at 12 months

Secondary Objectives:

- To evaluate the effect of SWiM versus standard care on weight at 6 and 24 months
- To evaluate the effect of SWiM versus standard care on body composition, glycated haemoglobin (HbA1c), psychological well-being, and psychosocial outcomes at 6, 12, and 24 months.
- To evaluate whether the effectiveness of SWiM is moderated by demographic characteristics (PROGRSS-Plus criteria)²⁵ of participants or the weight loss intervention used to lose weight or amount of weight lost before joining the trial.

Process Evaluation Objectives

- To examine how the programme works (i.e., mechanisms of action).
- To explore how SWiM is perceived, experienced, and applied over time across individual contexts.
- To explore why components of SWiM work or do not work, and under what contexts.
- To explore what additional unintended outcomes (positive/negative) are experienced.
- To examine the extent to which SWiM is delivered as intended.
- To understand the contextual factors influencing the delivery of SWiM, by exploring health coaches' perceptions and experiences of delivering SWiM, including barriers and facilitators to delivery.

The NICE NG246 guideline calls for more research on weight management interventions in ethnic minority groups. This study will aim to address this gap by exploring differences in intervention effects across demographic groups.

Cost-Effectiveness Objectives

- To estimate the effect of SWiM versus standard care on health care utilisation, out of pocket spend on weight management services, and work productivity at 6, 12 and 24 months.
- To model the long-term cost-effectiveness of SWiM and its impact on health outcomes and related health care costs
- To evaluate whether the long-term cost-effectiveness of SWiM is different depending on initial weight loss or weight loss programme.
- To evaluate whether the long-term cost-effectiveness of SWiM differs by demographic characteristics.

3. METHODS

3.1 Study design

This is a pragmatic, randomised, single-blinded, parallel group trial with 1:1 randomisation. Participants will be randomised to either the acceptance-based weight maintenance programme (SWiM) or to standard care using a computer-generated sequence with 1:1 allocation stratified by weight loss programme and weight loss medication usage. Participants will complete assessments at baseline, 6, 12 and 24 months using remote measures.

3.2 Eligibility Criteria

We will recruit UK adults (N=1,840) with obesity or overweight who have, in the previous 6 months, completed at least 60% of one of 5 weight loss programmes currently commissioned by the UK NHS or local authorities:

- 1. Tier 2 weight management programme
- 2. Tier 3 weight management
- 3. NHS Diabetes Prevention Programme
- 4. NHS Digital Weight Management Programme
- 5. NHS Diabetes Remission Programme

Other inclusion criteria

- Age ≥18 years
- Capable of giving informed consent
- Good understanding of the English language (the intervention and study materials are not tailored to support non-English language speakers)
- Willing to be randomised
- Willing to complete study measurements
- Able to access the web-based platform from home

Exclusion criteria

- Current use of insulin
- Previous or planned bariatric surgery
- · Current or planned pregnancy
- Current diagnosis of eating disorder
- A same household partner

The Study Team reserves the right to withdraw a participant at any time if they don't follow the protocol.

3.3 Procedures

3.3.1 Recruitment

We will collaborate with weight loss programme (WLP) service providers and commissioners to recruit individuals who have completed their WLPs using established recruitment methods and materials.

Potential participants will receive a study information leaflet from the WLP via email or SMS. Those willing to participate will be asked to complete a webform to express their interest in taking part. The webform will assess eligibility and collect contact details. The webform link will be included in the study information leaflet and may also be sent to interested individuals by the WLP via email or text message. Participants can proceed directly to the participant information and e-consent webform or take more time to consider. They can also request the study team to contact them for further information.

The study information leaflet will contain the study team's contact details (telephone and email) so interested individuals can reach out with questions. With participant consent, the WLP may provide contact details to the study team, who will then send the information leaflet and a link to the eligibility screening form.

Service providers will be encouraged to promote the study in person and actively encourage participation. However, they will also conduct blanket SMS or email outreach to all eligible individuals. All providers will receive the same recruitment materials and be asked to follow the same protocols. While opportunistic in-person referrals by coaches or group leaders are encouraged, they are difficult to mandate or monitor. As a result, we rely on the goodwill and motivation of individual service providers to facilitate this aspect of recruitment.

3.3.2 **Consent**

If participants are interested in taking part, they will be sent a secure weblink which will be used to provide participant information, confirm eligibility, and obtain informed e-consent. Once informed consent is obtained, the study team will contact participants to address any follow-up questions, outline next steps, and collect baseline data.

3.3.3 Study measures

Participants will complete online assessments at baseline (0 months), 6, 12, and 24 months. Details of which measures will be taken at each appointment are summarised in Table 1. Participants will be given a gift voucher for completing online assessments (£10 for the 6-month assessment, £20 each for the 12- and 24-month assessments). Honoraria for assessment completion are independent of intervention attendance or completion. Where participants are unwilling to complete the full assessment, a reduced amount (£10) will be offered for completion of a minimal data questionnaire (primary outcome and key process data).

Table 1. Schedule of Enrolment, Interventions, and Assessments

	STUDY PERIOD				
	Enrolment	Baseline	Follow Up		
TIMEPOINT**	-t ₁	0	6 months	12 months	24 months
ENROLMENT:					
Eligibility screen	Х				
Informed consent		Х			
Randomisation		X (after baseline assessmen t)			
INTERVENTIONS:					
Supporting Weight Maintenance (SWiM)		•	-		
Standard Care		Х			
ASSESSMENTS:					
Height		Х			
Weight		Х	Х	Х	Х

Self-Report Questionnaires	Х	Х	Х	Х
HbA1c	Х	Х	X	X

Weight

At baseline, participants will be asked to report their height, and measure and report their weight, on the day that they complete the outcome assessment. Participants will be provided with a set of weighing cellular-scales (Withings BodyPro2). The scales are pre-configured before sending, and report weight measures over cellular data networks, and do not require a wi-fi connection or digital literacy to use. When participants stand on the scales, data is sent automatically to Withings' GDPR compliant servers in the EU and then retrieved using the Withings developer API directly to the MRC Epidemiology Unit's secure research data server. Data transfers are secured using HTTPS and OAuth2.0 authentication. Instructions for self-weighing will be provided to reduce measurement bias. Eligibility screening will assess the suitability of the scales. Participants with a pacemaker, defibrillator, or other electronic implant will receive the BodyPro scale instead, as it does not use bioelectrical impedance. Participants living in areas with poor cellular network connectivity or weighing over 200kg will receive a suitable medical-grade scale and will be contacted by the study team to report their weight. All participants will be asked to self-report weight in questionnaires (see Table 2) at each assessment as a back-up.

HbA_{1c}

HbA_{1c} will be measured with freepost finger prick home testing kits (provided and analysed by The Doctors Laboratory (TDL), United Kingdom, accredited to the international standard for medical laboratories, ISO15189),) which we used successfully in a previous trial.²⁶ The kits will include all of the equipment provided for participants to complete the test at home. Kits will then be posted back via freepost to the TDL team to analyse the samples. No identifiable information will be shared with the TDL team.

Questionnaires

Self-reported questionnaires will be collected via REDCap web surveys, with paper or telephone options available for participants requiring them. Self-reported behavioural and psychosocial measures will be collected via validated questionnaires. Health outcomes and use of health care, medications and weight management services will be collected via self-report.

A full list of questionnaires can be found in Table 2.

Table 2. Full list of questionnaires

Domain	Outcome	Measure	Time point
Clinical	Height	Self-measured	0m
Outcomes	Weight	Self-measured	0m; 6m; 12m; 24m
	Body composition	Self-measured	0m; 6m; 12m; 24m
	HbA1c	Self-measured	0m; 6m; 12m; 24m
Quality of Life	Health-related quality of	EQ-5D-5L ²⁷	0m; 6m; 12m; 24m
and Wellbeing	life		
	Wellbeing	The Short Warwick-	0m; 6m; 12m; 24m
		Edinburgh Mental	

	1	T	
		Well-being Scale (SWEMWBS) ²⁸	
Economic Evaluation	Health Care Use	MODRUM core module with depth questions for medications ²⁹	0m; 6m; 12m; 24m
	Out of pocket weight loss management costs	Selected modified MODRUM depth questions	0m; 6m; 12m; 24m
	Work productivity and impairment	Work Productivity and Impairment Questionnaire ³⁰	0m; 6m; 12m; 24m
Psychosocial factors	Emotional eating	TFEQ-R21 ³¹	0m; 6m; 12m; 24m
	Binge eating	Binge Eating Scale (BES) ^{32,33}	0m; 6m; 12m; 24m
	Experiential avoidance/psychological flexibility	Acceptance and Action Questionnaires (Weight Related) ³⁴	0m; 6m; 12m; 24m
	Depression	Patient Health Questionnaire 8-item (PHQ-8) ³⁵	0m; 6m; 12m; 24m
	Anxiety Stress	Generalized Anxiety Disorder 7-item (GAD-7) scale ³⁶	
	011033	Perceived Stress Scale (PSS-4) ^{37,38}	
Other	Physical activity	International Physical Activity Questionnaire (IPAQ) - Short Form Short form ³⁹	0m; 6m; 12m; 24m
	Sleep quality	Brief version of the Pittsburgh Sleep Quality Index (B- PSQI) ⁴⁰	0m; 6m; 12m; 24m
	Diet intake	Rapid Prime Diet Quality Score Screener (rPDQS)	0m; 6m; 12m; 24m
	Weight management questionnaire	Use of weight loss medications and other weight management programmes/activities used in addition to the allocated interventions	0m; 6m; 12m; 24m

Demographics	Bespoke	0m
	demographics	
	questionnaire based	
	on Progress-Plus	
	criteria (place of	
	residency,	
	race/ethnicity,	
	occupation,	
	gender/sex, religion,	
	education,	
	socioeconomic status,	
	social capital, age,	
	disability, relationship	
	status, caring	
	responsibilities, car	
	ownership, access to	
	the internet). ²⁵	

The study coordinator will send email or phone reminders to participants if a completed questionnaire is not received within seven days.

Participants will provide consent for future follow-up through routine data sources and national registries. NHS numbers will be obtained to facilitate this process.

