3.5 Outcomes

3.5.1 **Primary Outcome**

12-month change from baseline in weight (kg)

3.5.2 **Secondary Outcomes**

- 6 and 24-month change from baseline in weight (kg)
- 6, 12 and 24-month change from baseline in HbA1c, emotional eating, binge eating, psychological flexibility, anxiety symptoms, depression symptoms, wellbeing, physical activity, diet, sleep quality (all outcomes outlined in Table 2).

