8	Session 8: Forming Helpful Habits	30-minute scheduled telephone call following completion of SWiM Session 8	
9	Session 9: Breaking Unhelpful Habits		
10	Session 10: Urges and Cravings		
11	Session 11: The Power of Sleep		
12	Session 12: Friends and Family		
13	Session 13: Weight Stigma and Body Image		
[4-week break to practice skills]			

		30-minute scheduled telephone call
17	Session 14: Lapses and motivation	following completion of SWiM Session
.,		14.

Web Platform

On the SWiM web platform, intervention content is divided into SWiM sessions, which are each divided into activities. Progress through the sessions is presented as a 'journey' using a map-like graphic. Star icons "light up" when activities/sessions are completed (Figure 2). As participants complete core skills exercises, these are stored in "SWiM Tools," where they can be accessed without revisiting specific sessions.

The web platform is designed to allow participants to revisit past sessions and skills, and it is intended that future rollout would include indefinite access to the website.

Figure 1: Screenshot of participant 'journey' page of SWiM website

The web platform includes a weight tracker, which tracks weight over time, displayed in a visual graphic. The weight tracker generates a line graph that automatically updates as data is entered by the participant.

As part of the first session, participants are asked to enter their prior weight loss so they can see what they have already achieved. The weight tracker automatically sets a weight maintenance target range with a boundary of ± 3 kg, which they are encouraged to stick within. This boundary can be adjusted if required as weight changes over time.

Each session starts with a reflection on the previous session and SWiM practice and the entry of weight data into the tracker. Participants will be given the option of a printed booklet of the website exercises if they prefer to write their answers down rather than enter the information

SWiM 2.0 Study Protocol ISRCTNxxxxxxx

online. The "SWiM Tools" and a weight tracker graph will be included at the back of the workbook.

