5. STATISTICS AND QUANTITATIVE DATA ANALYSIS

5.1 Sample Size

Previous meta-analyses suggest weight gain prevention interventions achieve effects of ~1.5kg at 12 months (less weight gain compared with controls). Our feasibility trial observed a -3.86kg (95%CI: -7.83 to 0.11kg, p=0.06) difference in weight at 6 months between SWiM participants and standard care, with SWiM participants losing ~2.2kg whereas standard care participants gained ~2.2 kg. Our expert elicitation workshop identified a potential mean difference of -1.96kg at 12 months with considerable uncertainty. Pre-trial modelling suggests interventions achieving these differences in weight regain after weight loss, and potentially even smaller differences, should be cost-effective. Thus, we designed the trial to detect a small overall effect size of ~1kg.

With 1,840 participants there is 90% power to detect a 1.01 kg difference in mean weight between SWiM and standard care as significant at the 2-sided 5% level, assuming a standard deviation at baseline of 22 kg, a 0.967 correlation between baseline and follow up 46 and 30% attrition. The correlation between baseline and follow up is based on the SWiM feasibility study, and is corroborated by data from our previous studies including weight change in the first year after finishing a weight loss programme in the WRAP trial (r=0.96) and 9 month weight change in Fenland COVID (N=1162 adults with overweight/obesity, r=0.972).

Designing the trial to detect a small weight difference in the overall sample should also allow a reasonable level of power to detect differences between SWiM and control within each WLP group (e.g. among only those who lost weight with a tier 3 programme), or within specific demographic groups (e.g. among men). Assuming approximately 368 participants from each WLP, there would be 80% power to detect a 1.96kg difference as significant at the 5% level between SWiM and standard care within each WLP.

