14. PROGRAMME STEERING COMMITTEE

The Programme Steering Committee (PSC) will provide overall supervision for the SWiM 2.0 Trial on behalf of the Trial Sponsors (University of Cambridge) and Trial Funder (NIHR) and ensure that the project is conducted to the rigorous standards set out in the UK Policy Framework for Health and Social Care Research and the Guidelines for Good Clinical Practice. The Programme Steering Committee will also take on the role of Trial Steering Committee (this is a low-risk trial, and a separate Data Monitoring and Ethics Committee is not deemed necessary).

The PSC will provide advice to the Investigators on all aspects of the trial and will review and agree the trial protocol, the statistical analysis plan, and any amendments to the protocol. The PSC will be chaired by [name] (University of Bristol). Independent members include [name] (AstraZeneca, Statistician), [name] (National University of Ireland Galway, Health Economist), and [name] (PPI Advocate). This is a low-risk trial with no rules for early stopping and participants and study coordinators are not blind to intervention allocation. Thus, a separate data monitoring committee was not deemed to be necessary.

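### At 6 and 12 months the primary outcome can rest on unblinded self-reported weight, and follow-up reminders chase a missing questionnaire rather than a missing scale reading

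*Protocol*

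**What the plan says.** The primary outcome (Protocol section 3.5.1) is "12-month change from baseline in weight (kg"). Section 3.3.3 sets up an objective route: cellular scales that send each reading to the study server without the participant having to report it. The same section also allows weights that depend on what the participant says:

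- **Questionnaire weight, everyone.** "All participants will be asked to self-report weight in questionnaires (see Table 2) at each assessment as a back-up". The questionnaires can be completed on the web, on paper or by telephone.
- **Minimal-data form.** Those unwilling to do the full assessment are offered £10 for "completion of a minimal data questionnaire (primary outcome and key process data").
- **Non-cellular scales.** Participants with poor network coverage or weighing over 200 kg "will receive a suitable medical-grade scale and will be contacted by the study team to report their weight".

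After Table 2, section 3.3.3 has the coordinator send a reminder when a questionnaire is still outstanding after seven days. It describes no reminder for an absent scale reading.

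Section 14 records that "participants and study coordinators are not blind to intervention allocation", and section 3.4 says the same of the coordinator and data manager. Section 5.2 puts all available data into the primary analysis. Section 4.1 gives the SWiM arm coach calls and weekly self-weighing. It adds: "The weight tracker automatically sets a weight maintenance target range with a boundary of" ±3 kg. Under section 4.2, controls get no additional structured support.

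**The concern.** In an open trial, an automatically transmitted weight protects against reporting bias only when it is the value analysed. A typed or spoken weight depends on a participant who knows the allocation and, on the spoken route, possibly on staff who know it too. Only one arm has been coached on weight and given a target range, so the inclination to report a favourable figure may differ between arms. The design target is about 1 kg, so even a few tenths of a kilogram of arm-related misreporting would matter.

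Part of this is fixed when the data are collected. If nobody is prompted to step on the scale around the 12-month date, and no image of a non-cellular display is kept, then no objective value exists and no later analysis plan can recover it.

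**Working it through.** **Step 1. Reproduce the design figure.** Inputs from section 5.1: N = 1,840, SD 22 kg, baseline to follow-up correlation 0.967, attrition 30%, 90% power for 1.01 kg, tested "as significant at the 2-sided 5% level". Allocation is 1:1 (section 3.4).

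- Residual SD = 22 × √(1 − 0.967²) = 5.605 kg
- Analysed per arm = 1,840 × 0.70 / 2 = 644
- SE of the difference = 5.605 × √(2/644) = 0.312 kg
- Power = Φ(1.01/0.312 − 1.960) = 89.9%, against the stated 90%

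The sample size arithmetic is sound. What matters here is the SE of 0.312 kg.

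**Step 2. Where arm-related misreporting can enter.** Under section 3.4 baseline weight is provided before randomisation, so an error in it cannot depend on arm. Mixed instruments at baseline add noise only. The exposure is at 6 and 12 months.

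**Step 3. Bias formula.** Let f be the share of analysed 12-month weights that are self-reported (taken as equal in both arms), and d the between-arm difference in mean misreporting. Then bias = f × d. The two-sided rejection rate when there is no true effect is Φ(−1.960 − bias/SE) + 1 − Φ(1.960 − bias/SE). The documents give neither f nor d, so both are assumed.

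| f | d (kg) | Bias (kg) | Bias / 1.01 kg | Type I error |
|---|---|---|---|---|
| 10% | 0.5 | 0.05 | 5% | 5.3% |
| 10% | 1.0 | 0.10 | 10% | 6.2% |
| 20% | 1.0 | 0.20 | 20% | 9.8% |
| 30% | 1.0 | 0.30 | 30% | 16% |
| 30% | 1.5 | 0.45 | 45% | 30% |

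For the last row, 0.45/0.312 = 1.44 and 1 − Φ(1.960 − 1.44) ≈ 0.30.

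**Step 4. Unequal shares.** If the self-report share differs by arm, the bias is f₁m₁ − f₀m₀, where m is the mean misreporting in each arm. Equal misreporting would then still bias the contrast, in either direction. Weekly weighing is encouraged in one arm only, so unequal availability of scale readings is possible.

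**The case against.** The strongest reply is that nothing in the protocol is wrong or contradictory, and that much of the remedy is ordinary SAP content. Source precedence, visit windows, flagging and a sensitivity analysis may all be in the SAP, which is not at hand. That stands: their absence from the protocol is not a fault, and the point does not rest on it.

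Several stronger readings are tempting, but the documents do not support them.

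- A reader might infer that self-report replaces a missing assessment-day reading even when transmitted readings from nearby days exist. The protocol calls self-report a back-up, which puts the scale first, and it does not say that nearby readings are passed over. That self-report enters the primary model at all is itself an inference, from the back-up role, the content of the minimal-data form and the use of all available data.
- Contact by the study team might be taken as a fallback for a missed cellular reading. It is the planned route for a group identified at eligibility screening. That group's share should balance between arms, although its reporting could still differ by arm.
- Baseline weight might be thought exposed as well. Step 2 shows that it is not exposed to arm-related error.
- Misreporting might be expected to concentrate in the less engaged. The documents do not show this, and those participants are the least exposed to coaching. The last scheduled call is at week 17, well before 12 months.

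Automatic transmission, with no need for wi-fi or digital literacy, also favours a low self-report share. A back-up weight has real value against the assumed 30% attrition, so dropping self-report altogether would be the wrong response.

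**Conclusion.** The point holds as a limited weakness in data collection. At follow-up, unblinded self-report can feed the primary outcome by three routes, and the described reminders do nothing to obtain the objective reading in its place.

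The size cannot be derived from the documents. Under the assumed ranges (f 10-30%, d 0.5-1.5 kg) the bias is 0.05-0.45 kg, or 5-45% of the 1.01 kg target. It is negligible at the low end, and the top figure needs both upper limits at once. The range shows sensitivity and is not an estimate of the bias this trial will have. A change is still worth making because it is cheap and a later SAP cannot supply readings that were never collected.

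**What to change.** Amend Protocol section 3.3.3 as follows.

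1. **Prompt for the scale.** Whenever no transmitted reading has arrived, send both arms an identical prompt and reminder to step on the scale within a fixed window around each follow-up (for example ±4 weeks). Do this before a self-reported value is accepted, and include it in the minimal-data contact.
2. **Non-cellular scales.** Ask for a photograph of the display, uploaded to REDCap. Keep the reported value only if no photograph is supplied.
3. **Self-report as a flagged last resort,** so that no data are lost. Unless the SAP already does so, repeat the primary analysis without self-reported weights, and report self-report minus scale weight by arm. Everyone is asked to self-report and most will also transmit, so this comparison would replace the assumed d with trial data.

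The cost is protocol wording, an upload field, a reminder triggered by a missing reading, and one extra analysis. There are three downsides: slight extra burden on participants, some readings a few weeks from the assessment date, and possibly more readings available in the SWiM arm because it is encouraged to weigh weekly. The availability of transmitted readings should therefore be reported by arm.
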